7.4 PROTOCOL DEVIATIONS

Protocol deviations will be summarized in the CSR for the ITT population. This summary will include the number and percent of participants (overall and by site) with each deviation type. A listing of protocol deviations will be presented and will include deviation number, date deviation occurred, visit, type of deviation, description of deviation, and action taken.

7.5 MULTIPLE COMPARISONS AND MULTIPLICITY

To address the multiple primary endpoints defined in this study, the primary endpoints have been prioritized into a hierarchical structure. In order to test the primary symptom endpoint of Total OSDI, the primary sign endpoint of MGS must be statistically significantly higher in the 0.5% AZR-MD-001 treatment group compared to the vehicle treatment group using a two-sided significance level of 0.05. Using this strategy, the family-wise Type I error rate will be maintained at the 0.05 significance level for the two primary endpoints.

There will be no statistical adjustment of the significance level for multiple testing for the other efficacy endpoints as these comparisons will be descriptive in nature.

7.6 ASSESSMENT OF HOMOGENEITY

Tests of homogeneity across sites will be done to determine if the sites have reasonably homogenous responses. An analysis of covariance (ANCOVA) model will be performed for both the primary efficacy sign for MGD and primary efficacy symptom for MGD. For the primary efficacy sign for MGD, change in MGS score will be the dependent variable, baseline MGS score and duration of disease will be covariates, and the independent variables will consist of treatment group, site and a site*treatment group interaction term. For the primary efficacy symptom for MGD, change in OSDI will be the dependent variable, and baseline OSDI and duration of disease will be the covariates. A site*treatment

	TEMPLATE		
	DOCUMENT #:		TMP-191
	REVISION:		2.0
STATISTICAL ANALYSIS PLAN TEMPLATE	CC #:	836	PAGE 15 OF 25

group interaction that is significant at a 0.15 level will require further investigation of results by site to assess if sites are still poolable despite being significant at the liberal 0.15 level of significance.

In study sites with small numbers of subjects, it will be difficult to evaluate a site by treatment interaction. For this reason, study sites with fewer than 5 subjects may be combined into pseudosites. Pseudosites will be used for all multivariate analyses including the analysis to determine a site by treatment interaction for pooling. All pseudosite categorizations will be determined before the database is locked.

8 DEMOGRAPHICS AND OTHER BASELINE CHARACTERISTICS

In general, continuous data will be summarized with descriptive statistics (number of patients, mean, standard deviation, median, minimum, and maximum) and will be analyzed using analysis of variance (ANOVA) techniques or 2-sample t-tests for between-group comparisons, and paired t-tests for within group comparisons. Categorical variables will be summarized by sample size (N), frequency count, and percent, and they will be analyzed using Pearson's chi-square test or Fisher's exact test (if the expected cell count is less than 5 in 25% or more of the cells). Ordinal variables will be analyzed using the Cochran-Mantel-Haenszel (CMH) or the Wilcoxon rank-sum test for between-treatment comparisons and the sign-rank test for within-treatment comparisons.

8.1 DEMOGRAPHICS AND VITAL SIGNS

Participant demographics for the ITT, mITT, mITT2, and safety population will be summarized in a table. Sex, race, duration of MGD, and ethnicity will be summarized with frequency and percent. Age, height, weight, BMI, SBP, DBP and heart rate will be summarized with number of observations, mean, median, minimum, maximum and standard deviation.

8.2 BASELINE NON-OPHTHALMIC MEDICAL HISTORY

The frequency and percent of patients with relevant medical and surgical history for each body system (e.g. General, Respiratory, Cardiovascular) will be presented for the mITT population. A listing of medical history information will be presented with information regarding body system, relevant medical condition/surgery, and start and end date. The listing will also include information regarding if a urine pregnancy test was performed and the result.

8.3 BASELINE OPHTHALMIC HISTORY

	TEMPLATE		
	DOCUMENT #:		TMP-191
	REVISION:		2.0
STATISTICAL ANALYSIS PLAN TEMPLATE	CC #:	836	PAGE 16 OF 25

The frequency and percent of patients with relevant ophthalmic and surgical history by ocular disease / condition / procedure by will be presented for the mITT population. A listing of ophthalmic history will be presented with information regarding the eye/eyelid, the ocular disease / condition / procedure, any related current medication for the condition, and start and end date.

8.4 PRIOR AND CONCURRENT MEDICATIONS

All relevant prior and concomitant medications will be presented in a listing for the mITT population. Patients must have discontinued and be willing to remain off all other ophthalmic preparations including artificial tears during the study. In the event that rescue medication is required for clinically relevant worsening of keratitis, patients will be provided a concomitant regimen the investigator/treating clinician.

9 EFFICACY ANALYSES

9.1 PRIMARY EFFICACY SIGN FOR MGD

The primary sign for MGD is based on change from baseline in meibum gland secretion (MGS) score (0 to 45 scale) at the 3-month follow-up between AZR-MD-001 group versus vehicle group. The primary efficacy sign will be evaluated in the mITT and mITT2 populations and will be analyzed at month 3 using an analysis of covariance (ANCOVA) model with baseline MGS score and duration of disease stratum (< 5 years or ≥ 5 years) as covariates and treatment (AZR-MD-001 ointment/semi-solid drug or vehicle) as factors in the model. The difference between treatment groups will be evaluated using t-tests of the least square means from this model. The two-sided confidence interval (95%) will be provided for the difference between treatments.

The following pseudocode will be used:

```
PROC GENMOD data=xxx;
BY visit;
CLASS treatment (ref = 'AZR-MD-001 VEHICLE') duration;
MODEL chg = treatment base duration;
LSMEANS treatment;
run;
```

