#### 9.4.2 ANALYSIS OF THE PRIMARY EFFICACY ENDPOINT(S)

The primary efficacy variables (see Section 8.1.1) will be analyzed at month 3 using an analysis of covariance [ANCOVA] model with baseline MGS score and duration of disease as covariates and treatment (AZR-MD-001 ointment/semi-solid drug or vehicle) as factors in the model. Pairwise comparisons will be performed for each AZR-MD-001 ointment/semi-solid drug treatment group versus vehicle using t-tests of the least square means from this model. Two-sided confidence intervals (95%) will be provided for the differences between treatments.

Details of other efficacy analyses will be provided in the statistical analysis plan.

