7.1 ANALYSIS SOFTWARE

Analysis data sets, statistical analyses and associated output generated by Avania will be generated using SAS® Software version 9.4 or later, or R version 3.3.2 or later.

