9.2 PRIMARY EFFICACY SYMPTOM FOR MGD

The primary symptom for MGD is based on change from baseline in total OSDI at the 3-month follow-up between AZR-MD-001 group versus vehicle group. The primary efficacy symptom will be evaluated in

	TEMPLATE		
	DOCUMENT #:		TMP-191
	REVISION:		2.0
STATISTICAL ANALYSIS PLAN TEMPLATE	CC #:	836	PAGE 17 OF 25

the mITT and mITT2 populations and will be analyzed at month 3 using an analysis of covariance (ANCOVA) model with baseline OSDI, baseline MGS score stratum (<6 or ≥6) and duration of disease stratum (< 5 years or ≥ 5 years) as covariates and treatment group as factors in the model. The difference between treatment groups will be evaluated using t-tests of the least square means from this model. The two-sided confidence interval (95%) will be provided for the difference between treatments.

The following pseudocode will be used:

```
PROC GENMOD data=xxx;
BY visit;
CLASS treatment (ref = 'AZR-MD-001 VEHICLE') duration baseMGS;
MODEL chg = treatment base duration baseMGS;
LSMEANS treatment;
run;
```

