13 SUMMARY OF CHANGES FROM THE PROTOCOL

The following table provides a list of changes from the protocol to the SAP, and the justification for each change.

Section	Description	Justification
9 Efficacy Analyses	Removed reference to pairwise comparisons between treatment groups.	Throughout the protocol, there is reference to performing pairwise comparisons between treatment groups which is thought to be leftover from the AZ201801 study where there were more than 2 treatment groups. For this study, we will use LSMEANS to compare the two treatment groups, as applicable.

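### SAP 9.1 and 9.2 promise ANCOVA t-tests but print default PROC GENMOD code; run as printed at n=30, the primary tests would have alpha of about 8% to 9%, and the CMH code in 9.3.21 does not test treatment

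*SAP*

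**What the plan says.** Protocol 9.4.2 specifies an ANCOVA for both primary endpoints, with treatments compared "using t-tests of the least square means from this model" and a 95% confidence interval. SAP 9.1 (MGS) and 9.2 (OSDI) repeat this; in 9.1 the wording is "The difference between treatment groups will be evaluated using t-tests of the least square means from this model".

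Each of these SAP sections then says "The following pseudocode will be used" and prints a block that opens with "PROC GENMOD data=xxx". The block contains only BY, CLASS, MODEL and LSMEANS statements. The MGS model has treatment, baseline and duration. The OSDI model is "MODEL chg = treatment base duration baseMGS". The LSMEANS statement requests neither a difference nor confidence limits. Sections 9.3.2, 9.3.4 and 9.3.5 use the same construction.

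SAP 7.1 allows SAS "version 9.4 or later, or R version 3.3.2 or later". SAP 13, the list of changes from the protocol, records no change of test; it says "we will use LSMEANS to compare the two treatment groups, as applicable". SAP 7.5 makes MGS the gate for OSDI and claims that "the family-wise Type I error rate will be maintained at the 0.05 significance level for the two primary endpoints".

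SAP 9.3.21 says that CMH statistics will test for a treatment effect on lid-margin scores. Its PROC FREQ table request names treatment first, then baseline, then result. Section 9.3.22 (corneal and conjunctival staining) refers back to 9.3.21 and has no code of its own.

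**The concern.** The prose and the code describe different tests. An ANCOVA t-test divides the residual sum of squares by n − p and refers the statistic to t on n − p degrees of freedom. GENMOD fits by maximum likelihood and by default gives a Wald test against the normal distribution. In a large trial the gap is negligible. With about 30 patients and four or five mean parameters it is not.

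The stake is the primary conclusion. An MGS result with an ANCOVA p between 0.05 and about 0.08 would be declared significant from the default GENMOD output and would open the OSDI test. Two programmers following the same SAP could reach opposite conclusions, and the choice between them could be made after unmasking.

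The CMH problem is separate and lesser. The printed p-value would answer a different question from the one the text asks.

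**Working it through.** **Inputs.** Two-sided alpha 0.05 (SAP 7.5). Planned n about 30; 12 per group, hence n = 24, is the sample-size figure for MGS; about 15 patients in the stratum that forms mITT2 (SAP 4). Mean parameters from the printed models: MGS p = 4 (intercept, treatment, baseline, duration); OSDI p = 5 (MGS stratum added). In mITT2 the MGS stratum is constant, so p = 4 for both.

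**Software assumption.** Default GENMOD uses a normal model, maximum-likelihood scale (RSS/n) and a Wald z reference.

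**The plan's own figure.** With t on n − p degrees of freedom, alpha is 0.0500 by construction. Simulation of 40,000 null trials per endpoint at n = 30 gave 5.04% (MGS) and 4.97% (OSDI).

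**The code as printed.** The Wald statistic is z = t × √(n/(n − p)), so

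alpha = 2 × P(t on n − p df > 1.96 × √((n − p)/n)).

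- MGS, n = 30: 1.96 × √(26/30) = 1.825 on 26 df, alpha = 0.0796.
- OSDI, n = 30: 1.96 × √(25/30) = 1.789 on 25 df, alpha = 0.0857.
- MGS, n = 24: 1.96 × √(20/24) = 1.789 on 20 df, alpha = 0.0887.
- OSDI, n = 24: 1.96 × √(19/24) = 1.744 on 19 df, alpha = 0.0973.
- mITT2, n = 15: 1.96 × √(11/15) = 1.678 on 11 df, alpha = 0.1214.

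Simulation at n = 30 gave 8.1% (MGS) and 8.6% (OSDI).

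**Variants (MGS / OSDI, n = 30).**

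- Unbiased scale with z, 2 × P(t > 1.96): 0.0608 / 0.0612. At n = 24: 0.0641 / 0.0648. In mITT2: 0.0758. This needs a scale option that is not in the printed code.
- Likelihood ratio: 0.0707 / 0.0765.

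**Interval width.** The ratio of the ML z interval to the t interval is 1.96 × √((n − p)/n) / t(0.975, n − p).

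- n = 30: MGS 1.825/2.056 = 0.888; OSDI 1.789/2.060 = 0.869. The intervals are 11% and 13% too narrow.
- n = 24: 0.858 and 0.833, so 14% and 17% too narrow.
- Unbiased scale with z: ratios 0.936 to 0.954, so 5% to 6% too narrow.

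**Printed p-value.** An MGS ANCOVA p of exactly 0.05 at n = 30 has t = 2.056. Then z = 2.056 × √(30/26) = 2.208, and GENMOD prints p = 0.027. For OSDI the corresponding value is 0.024.

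**Family-wise rate.** Under the global null, the gate makes the family-wise rate equal to the MGS rate, about 8.0% at n = 30.

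**CMH order.** It is assumed from PROC FREQ behaviour that the first variable of a three-way table is the stratum. The request in 9.3.21 then relates baseline to result within each arm. Illustrative simulations at n = 30:

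- No treatment effect, equally frequent levels, baseline/follow-up correlation 0.3, 0.5 and 0.7 (coded order against baseline as stratum). Three levels: 0.11, 0.36, 0.76 against 0.05, 0.04, 0.04. Four levels: 0.09, 0.22, 0.65 against 0.05, 0.04, 0.03. Six levels: 0.05, 0.14, 0.34 against 0.02 throughout.
- A 2 SD treatment effect and no baseline association, three levels: the coded order rejects 4% of the time, against 98% with baseline as stratum.

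**The case against.** The strongest reply is that the text governs. The t-test appears in the protocol and in every relevant SAP section, SAP 7.3 and 7.6 again call the model an ANCOVA, and SAP 13 does not withdraw it. The block is labelled pseudocode, uses a placeholder dataset name and omits the option that would print the LS-mean difference. R is also allowed, where a SAS block cannot bind literally. This is probably what the authors intended, and if so alpha is nominal. But the SAP also says the code will be used and contains no precedence rule, so the defect stands as an unresolved choice of primary test.

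Three points of precision also stand:

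- Default GENMOD gives about 8% to 9%, and the figures near 6% need an option not in the code. At the planned n = 30 the figures are 8.0% and 8.6%; those at n = 24 describe the power minimum.
- The exact values assume normal errors with equal variances. Using the SAP's MGS standard deviations, 3.35 and 9.48, simulation at n = 30 gives about 5.6% for the t-test and between 8% and 9% for the ML z test. The gap of roughly three points persists.
- The CMH percentages depend on assumed levels and correlations. With no baseline/follow-up correlation, both orders reject in 2% to 5% of null trials. What does not depend on those assumptions is that the coded order does not test treatment.

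**Conclusion.** The concern holds and should be fixed. Text and code conflict on the primary test, and no statement resolves the conflict. If the text is followed, alpha is 0.05 under the usual ANCOVA assumptions. If the code is run with the assumed defaults, alpha at n = 30 is 8.0% for MGS and 8.6% for OSDI, and about 12% in the mITT2 sensitivity analysis. Every z or likelihood-ratio variant examined exceeds 5%. The LS-mean difference and an interval can still be read from the treatment coefficient, but they would be z-based. The family-wise claim in SAP 7.5 is therefore secure only if the text is followed.

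The CMH code in 9.3.21, and by reference 9.3.22, does not do what its text says, given the PROC FREQ ordering rule. Because SAP 7.5 calls the other efficacy comparisons descriptive, this does not affect the primary claim. Confidence is high on the mismatch and the arithmetic; whether the inflation occurs depends on which reading the programmer takes.

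**What to change.** Make these changes before unmasking:

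1. In SAP 9.1, 9.2, 9.3.2, 9.3.4 and 9.3.5, replace PROC GENMOD with PROC MIXED (`LSMEANS treatment / DIFF CL`) or PROC GLM (`LSMEANS treatment / PDIFF CL`), so that tests and intervals use t on n − p degrees of freedom.
2. Add one sentence: where text and pseudocode differ, the text governs, in SAS or R.
3. In 9.3.21, change the table request to `base * treatment * result / CMH`. Section 9.3.22 then inherits it.

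The cost is a few lines of code and one sentence, with no change to data collection, sample size or estimand. Primary p-values will be larger and intervals wider than GENMOD would have shown. The corrected CMH test can be conservative when baseline strata are sparse (about 2% rejection with six levels in the illustration), which is acceptable for descriptive endpoints.

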9.2 PRIMARY EFFICACY SYMPTOM FOR MGD

The primary symptom for MGD is based on change from baseline in total OSDI at the 3-month follow-up between AZR-MD-001 group versus vehicle group. The primary efficacy symptom will be evaluated in

	TEMPLATE		
	DOCUMENT #:		TMP-191
	REVISION:		2.0
STATISTICAL ANALYSIS PLAN TEMPLATE	CC #:	836	PAGE 17 OF 25

the mITT and mITT2 populations and will be analyzed at month 3 using an analysis of covariance (ANCOVA) model with baseline OSDI, baseline MGS score stratum (<6 or ≥6) and duration of disease stratum (< 5 years or ≥ 5 years) as covariates and treatment group as factors in the model. The difference between treatment groups will be evaluated using t-tests of the least square means from this model. The two-sided confidence interval (95%) will be provided for the difference between treatments.

The following pseudocode will be used:

```
PROC GENMOD data=xxx;
BY visit;
CLASS treatment (ref = 'AZR-MD-001 VEHICLE') duration baseMGS;
MODEL chg = treatment base duration baseMGS;
LSMEANS treatment;
run;
```

9.3 OTHER EFFICACY ANALYSES

All other efficacy endpoints will be summarized and analyzed in the mITT population unless otherwise stated.

9.3.1 MGS SCORE

The change from baseline to day 14, month 1, and month 1.5 in MGS score (0 to 45 scale) will be summarized using N, mean, standard deviation, median, minimum, and maximum.

The change from baseline will be analyzed at each visit in the same manner as described in Section 9.1.

9.3.2 MGS SCORE AT EACH VISIT

MGS score (0 to 45 scale) at each visit will be summarized in the mITT population using N, mean, standard deviation, median, minimum, and maximum.

The MGS score will be analyzed at each visit using an ANCOVA model with baseline MGS score and duration of disease stratum (< 5 years or ≥ 5 years) as covariates and treatment (AZR-MD-001 ointment/semi-solid drug or vehicle) as factors in the model. The difference between treatment groups will be evaluated using t-tests of the least square means from this model. The two-sided confidence interval (95%) will be provided for the difference between treatments.

The following pseudocode will be used:

	TEMPLATE		
	DOCUMENT #:		TMP-191
	REVISION:		2.0
STATISTICAL ANALYSIS PLAN TEMPLATE	CC #:	836	PAGE 18 OF 25

```

PROC GENMOD data=xxx;
BY visit;
CLASS treatment (ref = 'AZR-MD-001 VEHICLE') duration;
MODEL score =treatment base duration;
LSMEANS treatment;
run;

```

9.3.3 PROPORTION OF PATIENTS WITH MGS SCORE > 12 AT EACH VISIT

The proportion of patients with an MGS score > 12 at each visit will be summarized using shift tables displaying the frequency and percent of patients in each category (yes/no) by treatment group.

Logistic regression will be performed to compare treatments with respect to the proportion of patients achieving MGS score >12 at each visit, adjusting for baseline MGS score stratum and duration of disease stratum. The odds ratio, along with the 95% CI, for the treatment effect will be presented. Pearson's chi-square test, or Fisher's exact test (if the expected cell count is less than 5 in 25% or more of the cells), will also be performed.

The following pseudocode will be used:

```

PROC LOGISTIC data=xxx;
BY visit;
CLASS treatment (ref = 'AZR-MD-001 VEHICLE') duration baseMGS;
MODEL response =treatment base duration baseMGS;
LSMEANS treatment;
run;

PROC FREQ data=xxx;
BY visit;
TABLE treatment * response/EXACT;
ODS OUTPUT CHISQ = outc (where=(STATISTIC='Chi-Square'))
FISHERSEXACT=outf (where=(NAME1='XP2_FISH'));
Run;

```

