### 9.4.3 ANALYSIS OF THE SECONDARY ENDPOINT(S)

The secondary efficacy variables (see Section 8.1.2) will be analyzed using an analysis of covariance [ANCOVA] model with baseline MGS score and duration of disease as covariates and treatment (AZR-MD-001 ointment/semi-solid drug or vehicle) as factors in the model. Pairwise comparisons will be performed for each AZR-MD-001 ointment/semi-solid drug treatment group versus vehicle using t-tests of the least square means from this model. Two-sided confidence intervals (95%) will be provided for the differences between treatments.

Descriptive statistics (change from baseline variables) will be tabulated for the following within treatment group changes in the mITT population:

- Patients in the AZR-MD-001 ointment/semi-solid drug treatment group: changes from baseline to days 14, month 1, month 1.5 and month 3
- Patients in the AZR-MD-001 vehicle group: changes from baseline to days 14, month 1, month 1.5 and month 3

Within each treatment group, shift tables for complete treatment response (yes/no) in the study eye will be presented for patients in the mITT population for endpoint signifying a “clinical cure” (Proportion of patients with a MGS score > 12; Proportion of patients with a MGYLS score of >2; Proportion of patients with a MGYLOS score of >2; Proportion of patients with a TBUT > 5 seconds at each visit; Proportion of patients with a Schirmer’s test  $\geq$  10 mm at each visit; Proportion of patients with a Total OSDI < 13 at each visit; and Proportion of patients with a SPEED Score < 6.

- Patients in the AZR-MD-001 ointment/semi-solid drug treatment group: changes from baseline to days 14, month 1, month 1.5 and month 3.
- Patients in the AZR-MD-001 vehicle group: changes from baseline to days 14, month 1, month 1.5 and month 3.

The Logistic Regression method for general association, stratified by baseline MGS score and duration of disease will be used to compare treatments with respect to the proportion of patients achieving a “clinical cure” in the study eye. Odds ratio along with 95% CI will be obtained by pairwise comparisons will be performed for each AZR-MD-001 treatment groups versus vehicle..

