9.3.7 TBUT AT EACH VISIT

TBUT at each visit will be summarized and analyzed using the same methods as described in Section 9.3.5.

9.3.8 PROPORTION OF PATIENTS WITH TBUT > 5

	TEMPLATE		
	DOCUMENT #:		TMP-191
	REVISION:		2.0
STATISTICAL ANALYSIS PLAN TEMPLATE	CC #:	836	PAGE 20 OF 25

The proportion of patients with a TBUT score > 5 at each visit will be summarized and analyzed using the same methods as described in Section 9.3.3.

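### The SAP 9.3.3 logistic code, reused for all five responder endpoints, does not match its own text, names no modelled event and has no provision for separation, so it can return an inverted or non-estimable odds ratio

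*SAP*

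**What the plan says.** SAP 9.3.3 describes a logistic regression comparing treatments on the proportion with MGS > 12 at each visit, "adjusting for baseline MGS score stratum and duration of disease stratum". It continues: "The odds ratio, along with the 95% CI, for the treatment effect will be presented". An unadjusted Pearson or Fisher test is added, and shift tables give yes/no frequencies and percentages by treatment group.

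The code introduced as the code to be used reads "CLASS treatment (ref = 'AZR-MD-001 VEHICLE') duration baseMGS" and then "MODEL response =treatment base duration baseMGS", run by visit. A reference level is set for treatment. None is set for `response`, and its coding is not given. `base` is not in the CLASS statement, so it enters as a continuous term.

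The protocol's version (9.4.3) is a logistic regression "stratified by baseline MGS score and duration of disease will be used to compare treatments"; it has no further covariate. SAP section 13, the list of changes from the protocol, does not mention one.

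SAP 9.3.8 extends the method: "TBUT score > 5 at each visit will be summarized and analyzed using the same methods as described in Section 9.3.3". Sections 9.3.11 (SPEED < 6), 9.3.18 (OSDI change > 4.5) and 9.3.19 (OSDI < 13) do the same. SAP 7.1 allows SAS or R. SAP 7.5 calls the non-primary comparisons descriptive and makes no multiplicity adjustment for them.

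**The concern.** A reader of the study report will take the adjusted odds ratio and its interval as the summary of each responder endpoint. Three features of the code put that summary at risk.

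- **Direction.** By default PROC LOGISTIC models the lower ordered level of the outcome. With 0/1, N/Y or No/Yes coding that level is non-response, so the printed odds ratio is the reciprocal of the one the text describes. R's usual binomial fit models the second level. The same plan could therefore give reciprocal results in its two permitted packages.
- **Covariates.** Code and text specify different models. For MGS > 12, baseline MGS enters twice, once as a score and once as its own stratum.
- **Estimability.** With about 15 patients per arm and four or five parameters, a binary outcome can be completely or quasi-completely separated. Maximum likelihood then has no finite solution for at least one coefficient. If treatment is involved, no usable odds ratio or interval exists. The plan does not say what is reported instead, so the choice would be made after seeing the data.

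**Working it through.** **1. Code against text.** The 9.3.3 text and protocol 9.4.3 name treatment, MGS stratum and duration stratum. The code has these plus `base`. In SAP 9.3.4 and 9.3.5 the text does name the endpoint's baseline value beside the two strata, so its absence from the 9.3.3 text is a real discrepancy.

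**2. Size of an inversion.** Assumed response rates: 50% active, 20% vehicle.
- Odds ratio for response: (0.5/0.5)/(0.2/0.8) = 4.0.
- Odds ratio for non-response: 1/4.0 = 0.25.
- At 40% v 20%: (0.4/0.6)/(0.2/0.8) = 2.67, against 1/2.67 = 0.37.

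**3. The plan's own figure.** The documents give no response rates and no power for these models. Their nearest figure is the MGS sample size (SAP 4): 12 per group, difference 10.4, SDs 3.35 and 9.48, 90% power. The standard error is √((3.35² + 9.48²)/12) = 2.90 and the noncentrality is 10.4/2.90 = 3.58. Power with Welch degrees of freedom is 91.4% at 12 per group and 88.4% at 11, so 12 reproduces. These inputs can therefore be used to build MGS > 12.

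**4. Separation, by simulation.** Inputs from the documents: about 30 randomized, 1:1, half in each MGS stratum. Assumptions: integer baseline MGS uniform within stratum, duration stratum 50/50, 1,000 trials per setting. In the fixed-rate rows response does not depend on baseline. In the MGS rows, month-3 MGS is baseline plus a normal change, with SD 3.35 for vehicle and 9.48 for active unless stated. Linear programming checks first for any separation, then whether a separating direction involves the treatment coefficient.

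| Vehicle v active | Any separation, coded model | Treatment OR not finite, coded model | Treatment OR not finite, text model (no `base`) |
|---|---|---|---|
| 5% v 20% | 62.2% | 50.2% | 48.7% |
| 5% v 40% | 46.6% | 44.5% | 44.3% |
| 10% v 30% | 29.1% | 23.1% | 22.5% |
| 10% v 40% | 22.8% | 19.7% | 19.6% |
| 20% v 40% | 5.8% | 3.7% | 3.5% |
| 20% v 50% | 4.9% | 4.1% | 4.0% |
| 30% v 50% | 1.0% | 0.7% | 0.7% |
| MGS change 0 v 10.4 | 32.7% | 32.6% | 31.3% |
| MGS change 1.2 v 11.6 | 26.6% | 26.3% | 25.4% |
| MGS change 4.5 v 14.9 | 26.2% | 24.9% | 23.2% |
| MGS change 4.5 v 4.9 | 7.2% | 1.6% | 1.2% |
| MGS change 4.5 v 4.9, SD 7.11 in both arms | 3.2% | 0.9% | 0.8% |

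The three design-difference rows imply MGS > 12 in about 11% v 66%, 17% v 70% and 37% v 80%. The changes 4.5 and 4.9 are the protocol 2.2 month-3 means for vehicle and 0.5%. SD 7.11 is √((3.35² + 9.48²)/2).

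If response does depend on baseline MGS (log-odds slope 0.25 per unit, 1,500 trials per setting), the treatment odds ratio is not finite in 7.5% of fits at 20% v 50%, 25% at 10% v 40%, and 49% at 5% v 30%.

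**5. Number of fits.** Four endpoints at four post-baseline visits, plus OSDI change at month 3: 4 × 4 + 1 = 17.

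**6. Baseline visit.** The code runs by visit with no restriction. Eligibility at baseline requires MGS ≤ 12, SPEED ≥ 6 and OSDI ≥ 13, so MGS > 12, SPEED < 6 and OSDI < 13 have zero responders there and cannot be modelled. TBUT > 5 can occur, because the entry limit is 10 seconds.

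**The case against.** The best defence is that this is pseudocode. The text already says what is compared, namely the proportion achieving the response. A competent programmer would set the event level, and R would probably not invert the result. The shift tables would expose a wrong direction, and the Fisher test does not depend on the model. For the four non-MGS endpoints, adjusting for the endpoint's own baseline follows the pattern of SAP 9.3.4. The documents give no response rates, so separation cannot be called likely.

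Much of this stands:
- A reader might infer that the odds ratio as written would favour the wrong arm. The documents do not support that. Inversion needs SAS and a coding the SAP does not state, so it can happen but is not established.
- A reader might infer that separation is to be expected throughout. At moderate response rates, or at the prior-study changes, it is uncommon. Some separated fits also leave the treatment odds ratio finite.
- A reader might think that removing `base` cures separation. It barely changes the risk (26.3% to 25.4% at a change of 1.2 v 11.6).

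What does not stand is that nothing needs changing. The SAP says the code will be used, yet code and text specify different models. Neither the code nor a stated coding rule fixes the modelled level. The crude tables and the Fisher p-value do not supply the adjusted odds ratio and interval that 9.3.3 promises.

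**Conclusion.** The point holds as a defect of specification in five descriptive endpoints. The mismatch over `base` and the missing event level can be read directly from SAP 9.3.3. The size of an inversion, 4.0 printed as 0.25, is an illustration at assumed rates.

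The chance per fit that the treatment odds ratio has no finite estimate depends on response rates the documents do not give:
- about 24–33% for MGS > 12 if the design difference of 10.4 is real;
- about 20–50% if vehicle response is 5–10%;
- about 1–8% if rates lie between 20% and 50%;
- about 1–3% for MGS > 12 at the prior-study changes of 4.5 v 4.9.

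These figures rest on about 15 evaluable patients per arm and the baseline assumptions stated above; fewer patients would raise them. With up to 17 correlated fits, meeting at least one separated model is plausible, but the documents do not allow a firm probability.

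The primary MGS and OSDI analyses (SAP 9.1 and 9.2) use different models and are unaffected. The change should be made before unmasking, but the point does not threaten the trial's main conclusion.

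**What to change.** Amend SAP 9.3.3, and through it 9.3.8, 9.3.11, 9.3.18 and 9.3.19:

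1. State in the text that the modelled event is the responder level. Set it in the code whatever the coding, for example `response(EVENT='<responder level>')`, and require the same event if R is used.
2. Make code and text agree. Drop `base` for MGS > 12. For the other four endpoints either drop it or name the endpoint's baseline in the text, and record it in section 13 as a change from protocol 9.4.3.
3. Prespecify Firth penalised logistic regression with profile-likelihood intervals (`/ FIRTH CLODDS=PL`), at least whenever complete or quasi-complete separation occurs. Request the treatment odds ratio explicitly in place of the LSMEANS line.
4. Restrict the models to post-baseline visits.

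The cost is a few words of text and code. Firth estimates are shrunk slightly toward no effect. If Firth is only a fallback, the report should mark which estimates came from it.
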